7.5. Criteria for Study Termination

Unacceptable safety signals that prevent moving to the next higher dose cohort or result in stopping the study may include any of the following, if deemed to be related to study drug DE-122 (not DE-122 administration procedures):

- Pattern of systemic AEs
- Any of the following AEs in any 2 subjects in any cohort:
 - Retinal Non-perfusion of the study eye/vascular occlusion
 - Vasculitis
 - Retinitis
 - > 2+ disc edema
 - > 2 quadrants of retinal hemorrhage

7.6. Study Procedures

All subjects must sign a written ICF before participating in any study-related activity. Enrollment will occur at Visit 1 (Day 1) after a subject meets all eligibility requirements at Screening (Day -7 to Day -1) and Visit 1 (Day 1). Each enrolled subject will be assigned a unique subject number. If a subject is discontinued from the study for any reason, the subject number will remain in effect and will not be reused.

A Schedule of Events can be found below and detailed procedures for examinations can be found in [Section 21.4](#), Appendix D – Procedures for Examinations.

Table 4: Schedule of Events

Visit Number	Visit 0 (SCRN)	Visit 1		Visit 2	Visit 3	Visit 4	Visit 5	Visit 6	Visit 7	Visit 8 /Exit
		Pre	Post							
Visit Schedule (Time window; days)	D-7 to -1	D1		D2	D8 (±1)	D15 (±2)	D30 (±2)	D45 (±3)	D60 (±3)	D90 (±3)
Informed consent ^a	X									
Demographics/Eligibility	X	X								
Medical/surgical history, Concomitant medication	X	X		X	X	X	X	X	X	X
Physical exam	X									X
Vital signs	X	X		X	X	X	X	X	X	X
EKG	X				X		X			X
BCVA (ETDRS)	X	X		X	X	X	X	X	X	X
Slit-lamp biomicroscopy ^b	X	X	X	X	X	X	X	X	X	X
Intraocular pressure ^c	X	X	X	X	X	X	X	X	X	X
Indirect ophthalmoscopy ^b	X	X	X	X	X	X	X	X	X	X
SD-OCT	X	X		X	X	X	X	X	X	X
Fundus photography	X						X		X	X
Fluorescein angiography	X						X		X	X
Urine pregnancy test ^d							X		X	
Urinalysis ^e	X				X		X			X
Serum pregnancy test ^d	X									X
Hematology, chemistry serum sample ^e	X				X		X			X
Immunogenicity serum sample		X					X			
Biomarker serum sample ^f		X		X	X		X			X
DE-122 IVT Injection		X								
Rescue with anti-VEGF Injection ^g					(X)				(X)	
Anti-VEGF Injection ^h							X			
Adverse events		X	X	X	X	X	X	X	X	X

- Informed Consent Form - obtain prior to conducting any study-related activities.
- Slit-lamp biomicroscopy and indirect ophthalmoscopy will be performed prior to DE-122 or anti-VEGF intravitreal injection and within 30 minutes after injection.
- IOP will be performed before DE-122 or anti-VEGF Intravitreal injection and 40±10 minutes after injection. If IOP is increased ≥ 10 mmHg, repeat IOP measurement 60±10 minutes after the injection.
- Serum and urine pregnancy tests are to be performed on all women of child-bearing potential.
- Collect fasting urine and blood specimen.
- Biomarker serum sample will be collected from the subjects in Cohorts 3 and 4.
- If subjects meet the following rescue criteria at Visit 3 (Day 8±1) and/or at Visit 7 (Day 60±3): <5 letters gained from baseline BCVA or < 50 microns reduction from baseline CST as measured by SD-OCT.
- Subjects who do not receive rescue therapy with anti-VEGF medication at Visit 3 (Day 8±1) will receive anti-VEGF treatment at Visit 5 (Day 30±2).

7.6.1. Screening Phase

7.6.1.1. Visit 0/Screening (Day -7 to Day -1)

- Explain the purpose and details of the study to the subject and obtain written informed consent prior to the subject's participation in any study related activity.
- Obtain subject's demographic information, medical, surgical and medication history.
- Perform the following assessments: (all ophthalmic procedures to be performed OU)
 - Physical examination (if not performed by external internist)
 - Vital signs
 - EKG
 - BCVA (ETDRS)
 - Slit-lamp biomicroscopy
 - IOP
 - Indirect ophthalmoscopy
 - SD-OCT
 - Fundus photography
 - Fluorescein angiography
- Review the inclusion and exclusion criteria. Do not continue screening any subject who does not meet the screening eligibility requirements.
- If the subject continues to be eligible for the study, collect more than 8 hours fasting urine and blood specimen for the following examinations:
 - Urinalysis
 - Serum pregnancy test (for females of child-bearing potential)
 - Hematology, chemistry serum sample
- If subject has not been fasting, schedule the subject as soon as possible for fasting blood draw and urine specimen.
- Upload all collected images (SD-OCT, fundus photograph and fluorescein angiogram) to sponsor.
- Schedule the subject to return for Visit 1 (Day 1).

7.6.2. Treatment/follow-up phase

7.6.2.1. Visit 1 (Day 1)

- Review results of the following procedures performed at Screening (Day -7 to Day -1) to determine continuation in the study:

- Physical exam
- EKG
- Urinalysis
- Blood chemistry and hematology tests
- Serum pregnancy test (for females of child-bearing potential)
- If the subject continues to be eligible for the study, the following assessments must be performed prior to administration of DE-122 to confirm eligibility and obtain baseline characteristics:
 - Query for AEs
 - Update medical history and medications
 - Vital signs
 - BCVA (ETDRS)
 - Slit-lamp biomicroscopy
 - IOP
 - Indirect ophthalmoscopy
 - SD-OCT
 - Immunogenicity serum sample
 - Biomarker serum sample (in Cohorts 3 and 4)
- Perform final review of inclusion/exclusion criteria. If the subject meets all eligibility criteria, determine the study eye ([Section 14.1.5](#)), and then perform DE-122 administration.
- The following procedures must be performed for DE-122 administration ([Section 10](#)):
 - Prepare the DE-122 ([Section 10.4](#))
 - Load the syringe ([Section 10.5](#))
 - Prepare the eye including ocular antisepsis of study eye ([Section 10.6](#))
 - Administer DE-122 ([Section 10.7](#))
- The following assessments must be performed after the administration of DE-122:
 - Within 30 minutes following DE-122 injection
 - Slit-lamp biomicroscopy
 - Indirect ophthalmoscopy
 - IOP 40 (± 10) minutes following DE-122 injection
 - If post-injection IOP is increased ≥ 10 mmHg from pre-injection IOP, the IOP will be measured again 60 (± 10) minutes following injection. If there

is an increase of ≥ 10 mmHg at 60 (± 10) minutes post-injection compared to pre-injection IOP, the subject should be prescribed a topical IOP-lowering medication and monitored for resolution of the event by the Clinical Investigator. An IOP increase of ≥ 10 mmHg shall be reported as an AE.

- AE assessments must be performed after the DE-122 administration
- Upload all collected images (SD-OCT) to sponsor.
- Schedule the subject to return for Visit 2 (Day 2).

7.6.2.2. Visit 2 (Day 2)

- Perform the following assessments:
 - Query for AEs
 - Update medical history and medications
 - Vital signs
 - BCVA (ETDRS)
 - Slit-lamp biomicroscopy
 - IOP
 - Indirect ophthalmoscopy
 - SD-OCT
 - Biomarker serum sample (in Cohorts 3 and 4)
- Upload all collected images (SD-OCT) to sponsor.
- Instruct the subject to fast for a minimum of 8 hours prior to next visit.
- Schedule the subject to return for the Visit 3 (Day 8 \pm 1).

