21.4.14. Hematology, Chemistry and Urinalysis

Approximately 10 mL of fasting blood and urine samples will be obtained at Screening (Day -7 to Day -1), Visit 3 (Day 8±1), Visit 5 (Day 30±2) and Visit 8/Exit (Day 90±3). The subjects will be asked to fast for a minimum of 8 hours prior to each blood and urine collection. Samples will be sent to a central laboratory for analysis.

Serum Chemistry, Hematology

The following is a list of the minimum parameters that will be measured. Other additional parameters may also be reported.

Chemistry	Hematology
Albumin	red blood cells (RBC)
Creatinine	white blood cells (WBC)
lactate dehydrogenase (LDH)	differential WBC
glucose	platelets (PLT)
calcium	hemoglobin (HGB)
potassium	hematocrit (HCT)
sodium	mean corpuscular volume (MCV)
cholesterol (total, HDL and LDL)	mean corpuscular hemoglobin (MCH)
triglycerides	mean corpuscular hemoglobin conc. (MCHC)
urea nitrogen	
bilirubin (total, direct, indirect)	
alkaline phosphatase (ALP)	
alanine aminotransferase (ALT)	
aspartate aminotransferase (AST)	
gamma glutamyl transferase (GGT)	
Human chorionic gonadotropin (hCG)*	

Prior to enrolling a subject, the Clinical Investigator will indicate on the source document if any screening laboratory values exclude the subject from participating in the study (e.g., serum creatinine > 1.3 mg/dL).

*conduct only at Screening (Day -7 to Day -1) and Visit 8/Exit (Day 90±3).

Urinalysis

The following is a list of the minimum urine parameters that will be measured. Other additional urine parameters may also be reported.

Urinalysis
PH
Protein
Erythrocytes
Ketones
Glucose

Prior to enrolling a subject, the Clinical Investigator will indicate on the source document if any screening laboratory values exclude the subject from participating in the study.

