21.4.16. Procedure for Biomarker Serum Sample

Approximately 10 mL of blood sample will be collected for biomarker analysis from the subject at Visit 1 (Day 1), Visit 2 (Day 2), Visit 3 (Day 8±1), Visit 5 (Day 30±2) and Visit 8 (Day 90±3).

There will be up to 5 blood draws for Biomarker. The total amount of blood collected from each subject in Cohort 3 and Cohort 4 during this study will be approximately 50 mL.

Refer to the separate procedure manual for sample handling, storage, and shipment.

Table 6: Protocol Amendment 03 Summary of Changes

Page	Section Number and Title	Description of Change
4-8	2.SYNOPSIS	Modifications were made to reflect the study period and the study design changes made throughout the protocol.
16	5. INTRODUCTION	
Rationale: To update the status of the study.
 
Amendment 02 text: (None)
 
Amendment 03 text: As of June 2016, 2 subjects in Cohort 1 have been enrolled and completed the study with no adverse events, and no safety and tolerability concerns.

19	7.1. Overall Study Design and Plan.	
Rationale: To allow the cohort transition from Cohort 1 to Cohort 2 with 2 subjects safety data at least, according to the updated study status.
 
Amendment 02 context: Three subjects will be enrolled in Cohort 1. Three subjects safety data is required to make a decision by Safety Review Team whether or not the transition to Cohort 2 is acceptable.
 
Amendment 03 context: Two or Three subjects will be enrolled in Cohort 1. Two subjects safety data at least is required to make a decision by Safety Review Team whether or not the transition to Cohort 2 is acceptable.

20	Figure 1: Study Schematic	
Rationale: Updated in accordance with the change of overall study design and plan.

21	7.2. Number of Subjects	
Rationale: In accordance with the change of overall study design and plan and change of number of sites.
 
Amendment 02 text: Approximately 12 subjects (3 subjects per cohort) with refractory exudative age related macular degeneration will be enrolled at 3-4 sites. Amendment 03 text: Approximately 12 subjects (2 or 3 subjects in Cohort 1, 3 subjects each in Cohorts 2, 3 and 4) with refractory exudative age related macular degeneration will be enrolled at 5 sites.

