10. BIOMARKER ANALYSES

The following descriptive analysis is planned by dose level of DE-122:

- Individual Patient listing of biomarker level for each visit, both numeric and graph.
- Individual Changes from baseline in levels of biomarkers for each post-baseline visit, both numeric and graph.
- Summary analysis of above two by the two dose levels.

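### Fasting is instructed before the Day 8, 30 and 90 biomarker draws but not before the baseline draw, so 3 of the 4 planned changes from baseline compare samples taken under different instructions

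*Protocol*

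**What the plan says.** **Draws.** Protocol 21.4.16 begins its visit list "Approximately 10 mL of blood sample will be collected for biomarker analysis from the subject at Visit 1 (Day 1), Visit 2 (Day 2), Visit" and continues through Visits 3, 5 and 8. It adds "There will be up to 5 blood draws for Biomarker". Footnote f of Table 4 limits the sampling: "Biomarker serum sample will be collected from the subjects in Cohorts 3 and 4".

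**Fasting instructions.** Section 7.6.2.2 (Visit 2) ends with "Instruct the subject to fast for a minimum of 8 hours prior to next visit", which applies to Visit 3. Sections 7.6.2.4 (Visit 4) and 7.6.2.7 (Visit 7) repeat the line for Visits 5 and 8. Screening (7.6.1.1) closes only with "Schedule the subject to return for Visit 1 (Day 1", and Visit 1 (7.6.2.1) only with "Schedule the subject to return for Visit 2 (Day 2".

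**What fasting is tied to.** Section 21.4.14 covers the safety laboratory tests: "Approximately 10 mL of fasting blood and urine samples will be obtained at Screening (Day -7 to Day -1), Visit 3 (Day 8±1), Visit 5" and Visit 8. Section 11.2.10 gives the same four visits. In Table 4 the fasting footnote (e) sits on the urinalysis and hematology/chemistry rows. The biomarker row carries only footnote f. Section 21.4.16 sets no fasting condition.

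**Analysis.** Baseline is the last value before injection, at Visit 1 (SAP 4.2.2). SAP 10 plans "Individual Changes from baseline in levels of biomarkers for each post-baseline visit, both numeric and graph", along with listings of the levels themselves and summaries by the two dose levels.

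**The concern.** A change from baseline is easiest to read when both samples are taken under the same conditions. Here the instruction changes between Day 2 and Day 8, at the same visit for every sampled subject. A marker that moves with food could look flat on Day 2 and shifted from Day 8 onward, and a delayed drug effect could look the same.

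There is no control group, and Cohorts 1 and 2 give no biomarker samples. With about 6 subjects, the individual trajectories are essentially the whole result. Protocol 13.3 also keeps leftover serum to search for other biomarkers that are not named, so insensitivity to food cannot be assumed for every analyte.

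The safety laboratory tests do not have this problem. Their pre-dose sample at Screening is also fasting, and a subject who has not fasted is brought back. Table 6 shows that biomarker sampling was added by Amendment 03, to visits whose fasting lines follow the safety tests. No reason is given for treating the biomarker baseline differently.

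**Working it through.** **1. The plan's own figure.** Five draws (Visits 1, 2, 3, 5, 8) at about 10 mL each: 5 × 10 = 50 mL, which matches the total in 21.4.16. So there is 1 baseline sample and there are 4 post-baseline samples.

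**2. Draws against instructions.**

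| Biomarker draw | Fast instructed at the preceding visit? | Fasting safety tests at this visit? | On-study anti-VEGF before the draw? |
|---|---|---|---|
| Visit 1, Day 1 (baseline) | No | No | No |
| Visit 2, Day 2 | No | No | No |
| Visit 3, Day 8 | Yes (at Visit 2) | Yes | No; the draw is listed before the rescue step |
| Visit 5, Day 30 | Yes (at Visit 4) | Yes | Only in subjects rescued at Visit 3 |
| Visit 8, Day 90 | Yes (at Visit 7) | Yes | All subjects, at Visit 3 or Visit 5 |

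Three of the 4 changes (Days 8, 30 and 90) differ in fasting instruction from baseline. With 3 planned subjects in each of Cohorts 3 and 4, that is 6 × 3 = 18 of 6 × 4 = 24 individual changes.

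**3. Size of a possible bias.** Let δ be a marker's fed level minus its fasted level. The documents do not give δ, and it may be zero. Suppose k of n subjects happen to be fed at Visit 1 and all comply with the later fasts. With no drug effect, the mean change at Day 8, 30 or 90 is then −(k/n) × δ. For one cohort (n = 3):

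| k fed at baseline (assumed) | Shift in mean change |
|---|---|
| 0 | 0 |
| 1 | −δ/3 |
| 2 | −2δ/3 |
| 3 | −δ |

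The range is therefore 0 to −δ. The plan does not ask for k to be recorded, so the position in that range could not be recovered later.

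**4. Day 2 against Visit 1.** Fasting is uncontrolled at both visits. A subject fed at Visit 1 and fasted on Day 2 shifts by −δ, and the reverse gives +δ. This pair is not known to be like-for-like either.

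**5. After the fix.** With one fasting rule for all five draws, 0 of 4 changes differ in instruction.

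**The case against.** A reader might infer that the baseline samples are non-fasting, and that the three changes do mix a drug effect with a change in fasting state. The documents do not support that. A missing instruction leaves fasting unspecified; some subjects may arrive fasted. Nothing in either document says that endoglin-related proteins respond to food. Any calculation that starts from an assumed fasting shift shows only what that assumption implies.

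The other objections:

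- **The fasting sentence in 21.4.14.** It asks for a fast before every blood and urine collection and could be read to cover all draws. But it sits in the safety-test section, just after the list of Screening and Visits 3, 5 and 8. On the wide reading, Screening and Visit 1 would still lack the matching instruction, so the text would need aligning anyway.
- **The separate procedure manual.** It is not available for this review. The protocol cites it for handling, storage and shipment, not for preparing the subject.
- **Other contrasts in the data.** SAP 10 also shows levels at every visit. Days 8, 30 and 90 share the same instruction, so movement among them is not explained by it. This stands. A fasting shift would also cancel between 2.0 mg and 4.0 mg, but only if δ and the share fed at baseline were equal in the two cohorts. If 3 of 3 were fed in one and 0 of 3 in the other, the dose contrast would shift by a full δ.
- **Anti-VEGF.** It already limits attribution to DE-122 at Day 90 in all subjects and at Day 30 in rescued subjects. This stands, and standardizing fasting would not remove it. It does not help Day 8, which is where the fasting instruction first changes.
- **Importance.** Biomarkers appear in neither objective, are not among the endpoints in 14.1.1, and play no part in the dose-escalation criteria. The analysis is descriptive, and the study defines no hypothesis. This stands and keeps the severity low.

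**Conclusion.** The point holds in a limited form. Fasting is not standardized across the biomarker draws: 3 of the 4 planned changes from baseline compare a fasting-instructed sample with an uncontrolled one, in about 6 subjects. If a marker has a fasting effect, it could not be separated from a DE-122 effect in those changes. The possible bias in a cohort mean runs from zero to one full fed-minus-fasted difference, and the documents give no value for that difference. The count rests on the visit-by-visit text, with the fasting sentence in 21.4.14 read as belonging to the safety tests. The bias range also assumes that subjects comply with the later fasts. The consequence matters most on Day 8. This is a low-severity improvement to an exploratory analysis; it does not touch the primary or secondary objective.

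**What to change.** For Cohorts 3 and 4, give the existing 8-hour fasting instruction at Screening (7.6.1.1, for Visit 1) and at Visit 1 (7.6.2.1, for Visit 2). Add a note that applies to fasting blood only to the biomarker row of Table 4 and to 21.4.16. Do not reuse footnote e, because it also calls for urine and no urinalysis is scheduled at Visits 1 or 2.

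Alternatively, if fasting before those visits is unwelcome, record hours since last food at every biomarker draw and show it beside each value in the SAP 10 listing. Each change from baseline should then be interpreted in light of the recorded status, without assuming that any pair of visits is like-for-like.

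The cost is two more fasting visits for about 6 subjects, or one extra eCRF field. No dose, visit or eligibility rule changes.

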7.6.2.3. Visit 3 (Day 8 \pm 1)

- Perform the following assessments:
 - Query for AEs
 - Update medical history and medications
 - Vital signs
 - EKG
 - BCVA (ETDRS)
 - Slit-lamp biomicroscopy
 - IOP
 - Indirect ophthalmoscopy

- SD-OCT
- Urinalysis
- Hematology, chemistry serum sample
- Biomarker serum sample (in Cohorts 3 and 4)
- Upload all collected images (SD-OCT) to sponsor.
- Rescue therapy with anti-VEGF medication may be allowed at Visit 3 (Day 8±1) provided the following rescue criteria are met:
 - < 5 letters gained from baseline BCVA **OR**
 - < 50 microns reduction from baseline CST as measured by SD-OCT.
- Rescue therapy should be performed using the same anti-VEGF medication administered just prior to enrollment in the study. ([Section 9.2.2](#))
- If rescue is performed, the following assessments must be performed after the administration of anti-VEGF treatment:
 - Within 30 minutes following anti-VEGF treatment
 - Slit-lamp biomicroscopy
 - Indirect ophthalmoscopy
 - IOP: 40 (±10) minutes following injection
 - If post-injection IOP is increased ≥ 10 mmHg from pre-injection IOP, the IOP will be measured again 60 (±10) minutes following injection. If there is an increase of ≥ 10 mmHg at 60 (±10) minutes post-injection compared to pre-injection IOP, the subject should be prescribed a topical IOP-lowering medication and monitored for resolution of the event by the Clinical Investigator. An IOP increase of ≥ 10 mmHg shall be reported as an AE.
 - AE assessments must be performed after the anti-VEGF medication administration
- Schedule the subject to return for Visit 4 (Day 15±2).

7.6.2.4. Visit 4 (Day 15±2)

- Perform the following assessments.
 - Query for AEs
 - Update medical history and medications
 - Vital signs
 - BCVA (ETDRS)
 - Slit-lamp biomicroscopy

- IOP
- Indirect ophthalmoscopy
- SD-OCT
- Instruct the subject to fast for a minimum of 8 hours prior to next visit.
- Schedule the subject to return for Visit 5 (Day 30±2).

7.6.2.5. Visit 5 (Day 30±2)

- The following assessments must be performed prior to administration of anti-VEGF medication
 - Query for AEs
 - Update medical history and medications
 - Vital signs
 - EKG
 - BCVA (ETDRS)
 - Slit-lamp biomicroscopy
 - IOP
 - Indirect ophthalmoscopy
 - SD-OCT
 - Fundus photography
 - Fluorescein angiography
 - Urinalysis
 - Urine pregnancy test
 - Hematology, chemistry serum sample
 - Immunogenicity serum sample
 - Biomarker serum sample (in Cohorts 3 and 4)
- Upload all collected images (SD-OCT, fundus photograph and fluorescein angiogram) to sponsor.
- Subjects who did not receive rescue therapy with anti-VEGF medication at Visit 3 (Day 8±1) will receive anti-VEGF treatment. The anti-VEGF medication should be performed using the same drug received just prior to enrollment in the study ([Section 9.2.3](#)). If the subject received rescue therapy at Visit 3 (Day 8±1), anti-VEGF treatment and post-injection assessments are not necessary.
- The following assessments must be performed after the administration of anti-VEGF treatment:

- Within 30 minutes following anti-VEGF treatment
 - Slit-lamp biomicroscopy
 - Indirect ophthalmoscopy
- IOP: 40 (± 10) minutes following injection
 - If post-injection IOP is increased ≥ 10 mmHg from pre-injection IOP, the IOP will be measured again 60 (± 10) minutes following injection. If there is an increase of ≥ 10 mmHg at 60 (± 10) minutes post-injection compared to pre-injection IOP, the subject should be prescribed a topical IOP-lowering medication and monitored for resolution of the event by the Clinical Investigator. An IOP increase of ≥ 10 mmHg shall be reported as an AE.
- AE assessments must be performed after the anti-VEGF treatment.
- Schedule the subject to return for Visit 6 (Day 45 \pm 3).

7.6.2.6. Visit 6 (Day 45 \pm 3)

- Perform the following assessments:
 - Query for AEs
 - Update medical history and medications
 - Vital signs
 - BCVA (ETDRS)
 - Slit-lamp biomicroscopy
 - IOP
 - Indirect ophthalmoscopy
 - SD-OCT
- Upload all collected images (SD-OCT) to sponsor.
- Schedule the subject to return for Visit 7 (Day 60 \pm 3).

7.6.2.7. Visit 7 (Day 60 \pm 3)

- Perform the following assessments:
 - Query for AEs
 - Update medical history and medications
 - Vital signs
 - BCVA (ETDRS)
 - Slit-lamp biomicroscopy
 - IOP

- Indirect ophthalmoscopy
- SD-OCT
- Fundus photography
- Fluorescein angiography
- Urine pregnancy test
- Upload all collected images (SD-OCT, fundus photograph and fluorescein angiogram) to sponsor.
- Rescue therapy with anti-VEGF medication may be allowed at Visit 7 (Day 60±3) provided the following rescue criteria are met:
 - < 5 letters gained from baseline BCVA **OR**
 - < 50 microns reduction from baseline CST as measured by SD-OCT.
- Rescue therapy should be performed using the same anti-VEGF medication administered just prior to enrollment in the study ([Section 9.2.2](#)).
- If rescue is performed, the following assessments must be performed after the administration of anti-VEGF treatment:
 - Within 30 minutes following anti-VEGF treatment
 - Slit-lamp biomicroscopy
 - Indirect ophthalmoscopy
 - IOP: 40 (±10) minutes following injection
 - If post-injection IOP is increased ≥ 10 mmHg from pre-injection IOP, the IOP will be measured again 60 (±10) minutes following injection. If there is an increase of ≥ 10 mmHg at 60 (±10) minutes post-injection compared to pre-injection IOP, the subject should be prescribed a topical IOP-lowering medication and monitored for resolution of the event by the Clinical Investigator. An IOP increase of ≥ 10 mmHg shall be reported as an AE.
 - AE assessments must be performed after the anti-VEGF treatment
- Instruct the subject to fast for a minimum of 8 hours prior to next visit.
- Schedule the subject to return for Visit 8/Exit (Day 90±3).

